9.1 Reason of early termination

Possible reasons of early termination include, but are not limited to, the following:

- Withdrawal of informed consent: (For a research center which required its subjects to sign the ICF) a subject decided to withdraw from this study. The decision must be "determined by the subject himself/herself" and recorded in the subject's research file;
- Early termination of this study: The sponsor might decide to suspend this study in advance for any reason.

9.2 Early termination of this study by a subject

For a research center which required its subjects to sign the ICF, if a subject terminated this study in advance, the reason must be recorded in the source document and the file of the research center and submitted via CRF.

A subject who terminated this study in advance could not be replaced, and his/her data would be included in the results analysis, unless the subject submitted a written request to withdraw the data.

9.3 Early termination of this study by the sponsor

The sponsor had the right to temporarily suspend or terminate in advance the research of a single research center, multiple research centers, or all the research centers at any time. The reasons include but are not limited to: Security or ethical issues, inaccurate or incomplete data records, non-compliance, or unsatisfactory quantity or quality of enrollment.

If this study was terminated or suspended, the sponsor or its representative should follow applicable regulatory requirements to inform investigators/their organizations and regulatory authorities of the reason. The sponsor or investigators/their organizations should comply with applicable regulatory requirements to notify the Ethics Committees and submit the reason.

10 Statistical Methods

10.1 Primary endpoint

The primary endpoint of the study is:

Non-CSF infection within one year post implant.

Incidence of adverse events within one year post implant, which includes:

- Obstruction of a cerebral ventricular catheter
- Bactiseal Catheter slipping
- Poor position of a catheter
- Intestinal perforation, abdominal and pseudocysts, umbilical fistula, pseudo-acute appendicitis, infection, and ascites caused by catheter
- Subcutaneous twist, rupture, distal obstruction, and distal retraction from the abdominal cavity
- Failure of a Bactiseal Catheter
- Mechanical failure
- Obstruction or infection of the shunt path
- Leakage of CSF in an implanted Bactiseal Catheter
- Excessive drainage
- Damage of intracranial or abdominal tissue
- Fibrous adhesion related to distal catheter

10.2 General considerations

The primary analysis will be descriptive in nature and will be based on information in the data collection form.

The extraction of the data from the medical records will be done by the investigators who care for the patients; in this way, the possible limitation of the study that is normally observed in other studies of review of clinical histories in which the information can be interpreted incorrectly is minimized.

10.3 Sample size

This study would provide the non-infection rate of Bactiseal Catheter within one year and assure the acceptable threshold of 95% confidence interval (CI). If the sample size was N_0 at first, the uninfected patients t year later would approximately be:

$$N(t) = N_0 e^{-(r1+r2)t}$$

r1 and r2 represent the infection rate and the dropout rate.

The parameters of K-M survival analysis (e.g., non-infection rate) were estimated according to Peto. The two-sided confidence interval threshold of 95% of K-M survival t years after the operation was defined as S(t) in accordance with the following formula:

$$margin = 1.96 \sqrt{[S(t)]^2[1 - S(t)]/N(t)}.$$

According to a literature review, the annual infection rate of a catheter with antibiotics was 3.2% (95% CI 1.3-4.4%). By taking into account the differences among centers and of operating standards, the lower limit of 95% confidence interval of the infection rate was considered as the anticipated infection rate. The annual infection rate of a catheter with antibiotics was 4.3%. Therefore, the non-infection rate was 95.7% within one year. If 150 (100 subjects historical data from DPS-201501 study with additional 50 new subjects enrollment) subjects and the dropout rate was 10%, according to the first formula, the sample size of infected subjects one year after the operation, N(1), would be:

$$N(1) = N_0 e^{-(r1+r2)} = 150 * e^{-(0.044+0.1)} = 130.$$

The threshold of 95% CI of non-infection rate within one year would be:

$$margin = 1.96 \sqrt{[95.7\%]^2[1 - 95.7\%]/130} = 3.4\%.$$

The precision of 3.4% is considered acceptable for this study.

10.4 Criteria of qualification/disqualification of the trial results

This study aimed to collect post-marketing safety data on the Chinese population implanted Bactiseal Catheter, according to product registration requirements. It described the occurrence, type, severity, frequency of all AEs occurring during the research, as well as the correlation between AEs and the product. Hence, criteria of qualification/disqualification were not applicable.

10.5 Interim analysis

No interim analysis is planned for this study.

10.6 Analysis plan

All study data collected in this study will be presented in subject data listings. Statistical analyses will be performed using SAS 9.3 or later version. Other valid software might also be used as appropriate.

Data analysis will be carried out primarily using descriptive statistics. In general, mean, standard deviation, median, minimum and maximum will be calculated for continuous variables, and frequencies and percentages will be presented for categorical variables. If necessary, additional descriptive statistics may be calculated.

Analysis population

The primary analysis population for this study is the Per Protocol (PP) populations. The PP population will include all subjects who meet the inclusion/exclusion criteria

Subgroup analyses

The main subgroups that will be analyzed, in addition to the total population per protocol, will be adults and children.

Endpoint analysis

The primary endpoint of 1-year infection free survival rate will be estimated by the Kaplan-Meier method, the 95% confidence width for the survival rate will be estimated by the Peto method. The Kaplan-Meier survival curve will be presented.

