5.1 Endpoint

1. Non-infection rate of a subject within one year
2. Type and incidence of adverse events within one year of a subject

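### Section 10.6 specifies no estimator, denominator or confidence interval for one-year adverse-event incidence, and the default percentage would be modestly too low if records end before day 365

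*Combined protocol and SAP*

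**What the plan says.** Section 5.1 has two endpoints, the one-year non-infection rate and "Type and incidence of adverse events within one year of a subject". Section 10.1 places both under the primary endpoint; the second reads "Incidence of adverse events within one year post implant, which includes", followed by a list of twelve entries. Section 3.2 makes adverse events in the first year the basis for judging device safety.

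Under its endpoint analysis, section 10.6 names one method: "The primary endpoint of 1-year infection free survival rate will be estimated by the Kaplan-Meier method", with a Peto 95% interval. Adverse-event incidence is not mentioned there. What reaches it is the general descriptive rule, "frequencies and percentages will be presented for categorical variables", and a permissive clause, "If necessary, additional descriptive statistics may be calculated", which names nothing for adverse events.

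Three other places bear on the denominator and on follow-up:

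- Section 10.6 defines the per-protocol population by the eligibility criteria alone. Complete one-year records are not required.
- Section 9.2 keeps subjects who leave early in the analysis, without replacement, unless they ask in writing for their data to be withdrawn.
- Section 10.3 assumes that "the dropout rate was 10"%.

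Sections 7.4 and 8.5 take adverse events from existing medical records or a hospital database where there is one. Section 8.4 rules out any additional follow-up. Section 7.4 treats a death within the year as a complete case.

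**The concern.** Both endpoints are one-year incidences in the same subjects, drawn from the same records. The plan allows for incomplete follow-up when it sizes and estimates the infection endpoint, but says nothing about it for adverse events. A percentage over all eligible subjects treats anyone whose records stop early without an event as event-free to day 365. For a safety incidence that error runs towards too few events.

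Without a planned interval, the reader of the report, which section 10.7 says goes to the regulator in support of registration extension, would also not see how imprecise the adverse-event figures are. With the denominator left open, the direction of any bias cannot be read from the plan.

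**Working it through.** **Inputs from the plan (section 10.3).** Start size 150; dropout 10%, entered as a yearly rate of 0.1; anticipated infection, "The annual infection rate of a catheter with antibiotics was 4.3"%, so non-infection 95.7%.

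**The plan's own figures.** The plan prints "150 * e^{-(0.044+0.1)} = 130". Recomputed, 150 × exp(−0.144) = 129.9, which rounds to 130. The formula uses 0.044 where the text has 4.3%; with 0.043 the result is 130.0, so nothing turns on this. The margin is 1.96 × √(0.957² × 0.043 / 130) = 0.0341, the stated 3.4%. Both reproduce.

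**Assumptions not in the plan.** It gives no expected rate for non-infection adverse events, so I take true one-year incidences p from 5% to 50%. I assume a constant event hazard and independent dropout.

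**Percentage over all subjects.** With L = −ln(1 − p) and dropout rate d, the expected crude proportion is L/(L + d) × [1 − exp(−(L + d))].

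For p = 20% and d = 0.1: L = 0.2231; L/(L + d) = 0.6905; 1 − exp(−0.3231) = 0.2761; product 0.1907. If exactly 10% are lost by one year, d = −ln 0.9 = 0.1054 and the product is 0.1902.

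| True p | Crude, d = 0.1 | Relative shift | Binomial 95% half-width, n = 150 |
|---|---|---|---|
| 5% | 4.8% | −4.8% | 3.5 points |
| 10% | 9.5% | −4.8% | 4.8 points |
| 20% | 19.1% | −4.7% | 6.4 points |
| 30% | 28.6% | −4.6% | 7.3 points |
| 50% | 47.9% | −4.3% | 8.0 points |

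The half-width is 1.96 × √(p(1 − p)/150).

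**Sensitivity at p = 20%.**

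- *80% of events in the first quarter of the year.* The hazard is −ln(0.84)/0.25 = 0.697 in that quarter and −ln(0.80/0.84)/0.75 = 0.065 afterwards. With d = 0.1 the crude proportion is 0.1581 + 0.8193 × 0.0459 = 0.1957, a shift of −2.2%.
- *All 10% lost on day 0.* 0.9 × 0.20 = 0.18, a shift of −10%. This is the extreme.
- *No records lost.* No shift.
- *Heavier loss (assumed, not in the plan).* 20% lost gives 18.0%; 30% lost gives 16.9%.

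**Percentage over completers and event cases only.** The proportion followed to one year without an event is 0.80 × exp(−0.1) = 0.7239. The percentage is then 0.1907/(0.1907 + 0.7239) = 0.2085, which is above the true 20%. For a true 30%: 0.2863/(0.2863 + 0.6334) = 0.3113. The sign of the bias reverses.

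**The case against.** A reader might infer that the plan commits itself to crude adverse-event percentages over all subjects and that reported incidence is therefore too low. The documents do not support that. The sentence on percentages is a general default; it names neither the adverse-event endpoint nor a denominator, and the clause on additional statistics leaves room for more. The 10% is a planning input that appears only in the sample-size section. Every subject is at least one year past surgery at entry (section 6.2), deaths count as complete (section 7.4), consent withdrawal arises only at centres that require consent (sections 9.1 and 9.2), and the report follows one-year data collection on all subjects (section 10.7). If no records end early, there is no bias.

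The shift is also small. At a true 20% it is 0.9 points against a half-width of 6.4. The analysis is descriptive, and section 10.4 sets no pass or fail criterion, so no stated decision turns on it.

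These points stand, and they make the bias conditional and modest. They do not fill the gap. A year having passed since surgery does not mean a year of records exists when ascertainment is by chart only. The population definition and the retention of early leavers point to an all-subjects denominator, and the fact that another choice reverses the bias is itself a reason to state one. The imprecision that dwarfs the bias is also why an interval is needed.

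**Conclusion.** The point holds as a specification gap with a conditional bias. One-year adverse-event incidence has no estimator, denominator, censoring rule or interval of its own, while infection-free survival in the same subjects has a censoring-aware estimator and a 95% interval.

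Over the full per-protocol population, the default percentage would be low by 4% to 5% relative at the plan's assumed dropout, or 0.2 to 2.1 points across true incidences of 5% to 50%. This rests on constant hazards, independent dropout and my assumed event rates. How many records will actually end before day 365 cannot be known from the documents. This is a low-priority but inexpensive improvement.

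**What to change.** In section 10.6, for the first occurrence of any reportable adverse event and of each key event in sections 5.2 and 10.1:

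- Report cumulative incidence at day 365 with a 95% confidence interval.
- Treat death as a competing event (Aalen-Johansen). One minus Kaplan-Meier with deaths censored is not an equivalent option, because it overstates cumulative incidence.
- Censor at the last available record. Define that date once and use it for both the infection and the adverse-event analyses, since the plan currently defines it for neither.
- Keep raw counts and percentages alongside, stating the denominator and the number of subjects with complete one-year records.

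The cost is a little more programming and the collection of a last-record date; the timing of adverse events is already recorded under section 7.4. Reported incidences would be slightly higher than all-subjects percentages if records are lost, and intervals for rare events will be wide.

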3.2 Purpose

This study aimed to collect safety information from subjects implanted with a catheter (trade name: Bactiseal) produced by Codman & Shurtleff, Inc. of the United States. Device safety would be assessed based on all the adverse events that occurred within one year after the subjects were implanted with the catheter.

4. Research Design

This study was designed to be single arm, multi-center, and retrospective.

This is continued access study to enroll additional 50 new subjects, with total combined 150 subjects. The historical study is DPS-201501.

It would collect information on adverse events of subjects enrolled within one year after the implantation of Bactiseal Catheter from August 07, 2018 to August 31, 2019, through case review or hospital database (if any).

The following information would be collected from subjects' medical records:

1. General condition of the subjects
2. Intraoperative condition and catheter implantation
3. Information on the shunt product
4. Adverse events of subjects within one year after the operation and classification of the adverse events
5. Relevant examinations in case of postoperative infection
6. Other adverse event-related information (except anticipated adverse events)

Information on adverse events would be collected. And the safety of clinical application of the product would be assessed.

5. Endpoint

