6.2 Inclusion criteria

Subjects who met all of the following inclusion criteria would be enrolled:

1. The informed consent was exempted by the Ethics Committee of a research center. Or a subject or his/her legal representative signed the informed consent form (ICF) prior to the enrollment;
2. A subject had an indication suitable to use Bactiseal Catheter;
3. A subject received hydrocephalus shunt at least one year ago.

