10.7 Report

After the data of all subjects were completely collected (within one year after the operation), a clinical study report would be compiled and submitted to NMPA for review as material supporting the extension of product registration.

11 Research Management and Administration

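### The Peto interval in section 10.6 has zero width when no infection occurs, and with few infections it sets the upper limit for the infection rate too low

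*Combined protocol and SAP*

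**What the plan says.** Section 10.6 estimates one-year infection-free survival by Kaplan-Meier and adds that "the 95% confidence width for the survival rate will be estimated by the Peto method". Section 10.3 repeats the method ("The parameters of K-M survival analysis (e.g., non-infection rate) were estimated according to Peto") and gives the formula: half-width = 1.96·√(S(t)²·[1 − S(t)] / N(t)), where N(t) is the number left at time t. The interval is symmetric about S.

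For the expected rate, section 10.3 reports: "According to a literature review, the annual infection rate of a catheter with antibiotics was 3.2% (95% CI 1.3-4.4" per cent). It then plans on 4.3% infection, 150 subjects and 10% dropout.

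On the groups to be analysed, section 4 says "This is continued access study to enroll additional 50 new subjects, with total combined 150 subjects", while the proposal summary gives 50 subjects. Section 10.6 does not say which set the rate is estimated in. It adds: "The main subgroups that will be analyzed, in addition to the total population per protocol, will be adults and children". No subgroup sizes, no rule for zero events and no alternative interval are given.

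**The concern.** The formula contains the factor 1 − S. If a group has no infections, that factor is zero and so is the width, whatever the group's size. A group of 20 and a group of 150 would both be reported as 100% with no uncertainty. With a handful of infections the interval exists, but it is symmetric on a scale that ends at 100%. Part of it then extends above 100%, and the lower infection-free limit is too close to the estimate.

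Both faults err in the same direction: the device looks safer than the data can show. Section 10.4 sets no pass/fail criterion, so no decision rule fails. But section 10.7 says that "a clinical study report would be compiled and submitted to NMPA for review as material supporting the extension of product registration", and the infection-free rate with its interval is the reported result for the first primary endpoint.

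**Working it through.** **Inputs.** One-year infection rates of 3.2% and 4.3%, the literature range of 1.3–4.4%, 150 pooled subjects and 10% dropout (all section 10.3), and 50 new subjects (proposal summary, section 4). Subgroup sizes are assumed because the plan gives none. The Peto method is taken to be the formula in 10.3.

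**The plan's own figure.** N(1) = 150·e^−(0.044+0.1) = 129.9, and half-width = 1.96·√(0.957²·0.043/130) = 3.41%. The planned 3.4% reproduces.

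**No infections.** With S = 1 the half-width is 1.96·√(1·0/N) = 0. The exact upper infection limit with N at risk and no event is 1 − 0.025^(1/N): 7.1% for N = 50, and 7.9% for N = 45 (10% dropout).

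**Coverage with complete follow-up.** The number of infections k is binomial, S = 1 − k/n and N = n − k. The chance of no infection is (1 − p)^n. Coverage sums the binomial probabilities of every k whose interval contains p. Each cell gives the value at 3.2% / 4.3%.

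| n | P(no infection) | Peto coverage |
|---|---|---|
| 15 (assumed) | 61% / 52% | 38% / 48% |
| 25 (assumed) | 44% / 33% | 56% / 66% |
| 35 (assumed) | 32% / 21% | 68% / 78% |
| 50 | 19.7% / 11.1% | 80.2% / 88.4% |
| 75 (assumed) | 8.7% / 3.7% | 91% / 83% |
| 150 | 0.8% / 0.1% | 85.8% / 88.4% |

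Up to n = 50, coverage and P(no infection) add to almost 100%. Given at least one infection, coverage at these sizes is above 99%, so the shortfall there is the zero-infection case.

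**The pooled 150.** Zero infections is rare here and the cause is different.
- With 2 infections, S = 0.98667 and N = 148. The upper infection limit is 1.33% + 1.96·0.98667·√(0.01333/148) = 3.17%, just under 3.2%.
- With 3 infections, S = 0.98 and N = 147. The limit is 2.00% + 1.96·0.98·√(0.02/147) = 4.24%, just under 4.3%.

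So every sample with at most 2 (or 3) infections misses the true rate. These misses occur in 13.8% and 11.0% of samples, against a nominal 2.5%.

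**With dropout** (exponential, 0.10 per year, simulated with 20,000 runs). At n = 50, coverage is about 78% and 87%. At n = 150 it is 94% at both rates, because dropout lowers N and widens the interval slightly: with 2 infections the upper limit becomes 3.3%, which now covers 3.2%.

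**Average over 1.3–4.4%.** Single-rate figures at n = 150 jump in this way, so the average is the fairer summary. It is 89.9% without dropout (range 79.4–95.1%) and 90.1% with 10% dropout. About 9.5% of samples miss on the unfavourable side and 0.3–0.5% on the other. At n = 50 without dropout the average is 73.7%.

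**Alternatives over the same range.** Peto plus an exact limit at zero events averages 92.4% at n = 150 (93.2% with dropout). Complementary log-log plus that exact limit averages 96.0% at n = 50 without dropout, and 96.0% at n = 150 with or without it.

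**Lower infection-free limits, complete follow-up.** The complementary log-log limit is S^exp(θ) with θ = 1.96·√V/|ln S|, where V is the Greenwood sum. For 1/50, V = 1/(50·49), θ = 1.96, and the limit is 0.98^7.10 = 86.6%.

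| Infections | Peto | Complementary log-log | Exact |
|---|---|---|---|
| 1/50 | 94.1% | 86.6% | 89.4% |
| 2/50 | 90.6% | 84.9% | 86.3% |
| 2/150 | 96.8% | 94.8% | 95.3% |
| 6/150 | 92.9% | 91.3% | 91.5% |

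**The case against.** The plan sizes the study on 150 subjects with 10% dropout. There, coverage is 94% at both quoted rates and zero infections is very unlikely. The 86–88% needs no dropout at all: simulation gives about 90% with 2% dropout and 94–95% with 5%. This stands for those two rates. It does not remove the 90% average over the plan's range, nor the 6% of misses on the unfavourable side at 10% dropout.

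Low dropout is not assured either. Section 6.2 requires "A subject received hydrocephalus shunt at least one year ago", which guarantees elapsed time rather than documented follow-up, and sections 7.4 and 8.4 rely on existing records. So little dropout is plausible, but not established.

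At 50 or fewer, a zero-event rule alone would be enough for coverage: Peto with such a rule averages 99.8% at n = 50. That also stands. Its upper infection limit at 1/50 is still 5.9% against an exact 10.6%, and the rule does not repair the pooled 150.

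The replacement is not perfect. Its misses fall mostly on the other side: 4.0% against none at n = 50, and about 3.5% against 0.5% at n = 150. In very small subgroups its coverage can fall to about 90–91% at some rates. It is also wider than the exact limit at 1/50. With complete follow-up an exact interval would serve too, so the choice between them is partly preference.

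Finally, listings and counts would show a reader that there were no infections. That softens the harm but does not make the printed interval correct.

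**Conclusion.** The concern holds. The zero width follows from the plan's own formula and needs no assumption. At 50 subjects it would arise in roughly one sample in five at 3.2% infection and one in nine at 4.3%, and more often in smaller subgroups. At the pooled 150 the shortfall is moderate: about 90% average coverage instead of 95%, and close to nominal at the two quoted rates if dropout reaches about 5–10%. In every setting nearly all misses understate the possible infection rate.

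The result rests on reading the Peto method as the 10.3 formula and on that formula being used for whatever groups are reported. Section 10.6 does not state that it applies to the subgroups, and their sizes here are illustrative. The average weights the 1.3–4.4% range equally. The change should be made before analysis, but the flaw does not invalidate a descriptive study.

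**What to change.** In section 10.6, replace the Peto width by the Kaplan-Meier estimate with Greenwood variance and limits on the complementary log-log scale. For any group with no infections, report the Clopper-Pearson limit (0.025 tail), using the number still at risk at one year as the denominator. State that both rules apply to the total analysis set, naming whether that is the 50 or the 150, and to adults and children separately. Print the number of infections and the number at risk beside each interval. The Peto formula can stay in section 10.3 as a planning approximation.

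The cost is one or two sentences and standard software, with no new data. The reported lower limits become less favourable when events are few, by 7.5 points at 1/50 (94.1 − 86.6) and 1.6 points at 6/150 (92.9 − 91.3).
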